5.8. Exclusion Criteria

- 5.8.1. Patients with stones exceeding 20 mm in cumulative diameter on the side to be treated. *Note:* Punctate stones measuring ≤ 2mm do not count in the cumulative diameter limit.
- 5.8.2. Patients with ureteral stones located distal to the iliac vessels on the side to be treated
- 5.8.3. Diagnosis of radiolucent stones (on the side to be treated) on KUB or Scout CT Images
- 5.8.4. For patients who have a ureteral stent in place, patient is excluded if stent is calcified or encrusted as verified using standard of care imaging (e.g., KUBX-ray)
- 5.8.5. Patients who have had prior URS-LL within 3 months on the side to be treated at the time of consent
- 5.8.6. History of cystinuria
- 5.8.7. Urine pH is < 5.5. **Note:** If a patient's largest stone measures a mean stone intensity of ≥500 HU and the patient has a historical pH value of ≥ 5.5, a recently tested (within 30 days of consent) urine pH showing <5.5 in this case does not exclude a subject.
- 5.8.8. Patients with known history of recurrent uric acid stones.
- 5.8.9. Untreated urinary tract infection (UTI)
- 5.8.10. History of drug resistant chronic UTI
- 5.8.11. If female, pregnant as confirmed using urine or serum test to be conducted on the day of the procedure
- 5.8.12. Patient has an American Society of Anesthesiologists (ASA) physical classification level of 4 or greater.
- 5.8.13. Known sensitivity to possible medications used before, during, or after the URS laser lithotripsy procedure, including but not limited to the following: sedative agents, general anesthetics, topical anesthetics, and opioid analgesics
- 5.8.14. Stones suspected in calyceal diverticula
- 5.8.15. Horseshoe kidney
- 5.8.16. Congenital ectopic pelvic kidneys
- 5.8.17. Full staghorn calculi >2cm
- 5.8.18. Patients with elevated serum creatinine > 1.5mg/dl
- 5.8.19. Patients with solitary kidney
- 5.8.20. Malrotated kidney on the side with urinary stone
- 5.8.21. Duplicated collecting system or duplicated ureters
- 5.8.22. Patients who are currently involved in any investigational drug or device trial or have been enrolled in such trials within 30 days of index procedure
- 5.8.23. Patients who are actively taking antiplatelet and anti-coagulation except low dose aspirin
- 5.8.24. Prostate biopsy within the last 3 months
- 5.8.25. History of radiation therapy of abdomen and pelvis

CIP-0001(E) Acoustic Enhancer Research on Laser Lithotripsy (AEROLITH) Clinical Study DCO-326 EFFECTIVE DATE: 19 JAN 2022

CONFIDENTIAL Page 19 of 53

- 5.8.26. History of urinary tract reconstruction
- 5.8.27. Other factors that the investigator feels would interfere with the participation and completion of the study such as:
 - Inability to provide voluntary consent
 - Inability to understand the clinical investigation or cooperate with investigational procedures
 - Planned relocation or unable to return for required follow-up visits
 - Vulnerable individuals (mentally disabled, physically disabled, prisoner, etc.)

6. STUDY ENDPOINTS

6.1. Primary Safety Endpoint

The rate of occurrence of each arm of clinically significant serious adverse events defined as:

- Serious infection (urosepsis, pyelonephritis) requiring hospitalization and treatment through 90 days post index procedure
- New urinary tract stricture formation requiring surgical intervention through 90 days post index procedure

Confidence intervals will be presented to aid in the evaluation of the incidence of clinically significant serious adverse events, both for each treatment group individually, and for the difference in the rates between the two treatment groups.

6.2. Primary Efficacy Endpoint

Treatment success: Proportion of study subjects who have a complete absence of stone(s), or have residual fragments measuring to ≤ 2 mm, as assessed by CT imaging through 30 days follow-up post index procedure. CT imaging will be assessed by an independent core lab to determine treatment success. Treatment success, as defined by an absence of residual fragments >2mm on any dimension, has been identified as a priority in stone care in recent publications including Margaret Pearle's widely cited "Is Ureteroscopy as Good as We Think", published in the Journal of Urology in 2016 [12]. Increasing awareness and clinical prioritization of residual fragments in ureteroscopic laser lithotripsy derives in large part from expanded use of CT follow-up imaging in stone subjects. CT imaging has allowed characterization of residual fragments and full appreciation of their clinical significance, with rigorous studies of residual fragment natural history having established a 2mm threshold as a critical size above which additional stone events are particularly frequent [22], [23]. Therefore, the primary efficacy endpoint will demonstrate that the investigational arm (Acoustic Enhancer +_URS-LL) is superior in the fragmentation of stones to $\leq 2mm$ versus the control arm (URS-LL).

6.3. Secondary Efficacy Endpoint

Total radiant energy: Mean value of laser energy, measured in kilojoules, with laser energy values recorded and displayed by the pulsed laser unit used in the procedure, with the laser energy value for each procedure normalized by the stone cross-sectional area. For this purpose, the stone cross- sectional area is calculated by taking the product of the two largest stone size measurements on the pre-procedure CT; for subjects with more than one stone treated in the index procedure, the stone cross-sectional area is calculated as the sum of the stone cross-sectional areas calculated individually for each treated stone. The mean value of laser energy for each arm is calculated by considering the normalized measured values

for all study subjects in that arm.

Total radiant energy is an indicator of how effectively the laser has eroded, pitted and fragmented the stone over the course of the procedure, reflecting the contributions of the diverse mechanisms through which the laser acts on the stone [24]. With Acoustic Enhancer's being designed to improve stone erosion, pitting and fragmentation through the generation of additional stone-fragmenting shockwaves; therefore, the secondary efficacy endpoint will demonstrate non-inferiority of the mean TRE used between the investigational arm and the control arm.

6.4. Additional Observations

- 6.4.1. Mean total lasering time. While total radiant energy is a more rigorous and broadly applicable indicator of improved stone erosion, pitting and fragmentation through the generation of additional stone-fragmenting shockwaves, a demonstration of lower mean lasering time in the Acoustic Enhancer arm compared to the standard laser arm could be clinically important.
- 6.4.2. Additional interventional stone procedure(s) on stone(s) that were treated as part of the AEROLITH study.
- 6.4.3. Adverse Events (AEs) by type over time, severity, seriousness, and relatedness. AEs will be tabulated and summarized as counts and percentages. AEs will also be cross tabulated according to:
 - Severity
 - Unanticipated Adverse Device Effect (UADE)
 - Seriousness (Serious Adverse Event (SAE), Non-serious AE)
 - Device-Relatedness (Unrelated, Possibly Related, Probably Related, Definitely Related)
 - Procedure-Relatedness (Unrelated, Possibly Related, Probably Related, Definitely Related)

6.5. Measures to Increase Validity and Minimize Bias

- 6.5.1. Eligible subjects will be consecutively enrolled at each site. Reasons for screen failures will be documented.
- 6.5.2. Subjects will be blinded of their treatment allocation through index procedure.
- 6.5.3. Multiple sites will be utilized to ensure broad generalizability of results and minimize site effect.
- 6.5.4. CT image analysis will be performed by an independent core laboratory and they will be blinded to the treatment assignment. CT images will be obtained in accordance with guidelines specified in advance by the core laboratory.
- 6.5.5. The study monitor will review and verify data collection forms against source documentation to assure there are no missing, illegible, or incorrect data. Missing, illegible or incorrect data will be corrected following ICH/GCP guidelines.
- 6.5.6. The investigative site personnel will contact subjects prior to their scheduled study visits to increase compliance with the subject follow up protocol.

6.6. Study Success

The study is considered a success if the primary effectiveness endpoint is met with statistical significance and any safety findings are offset by the benefit in improved response when risks and benefits are weighed.

Statistical significance for the primary effectiveness endpoint is achieved when the one-sided p-value for the Farrington-Manning test when comparing the Treatment Success rates between the investigational arm (Acoustic Enhancer with URS-LL) and the control arm (URS-LL) is less than 0.025.

Statistical significance among any of the other effectiveness endpoints is *not* needed for Study Success.

7. STUDY PROCEDURES

7.1. Eligibility Review

Patients presenting with urinary stone disease will be screened for this study. Initial eligibility criteria for the study will be determined by the investigator based upon review of their medical history, presentation and diagnostic imaging. If the patient appears to meet the study criteria, the investigator will consent the patient accordingly.

7.2. Informed Consent Process

The informed consent document must comply with applicable regulatory guidelines (21CFR Part 50 and the Declaration of Helsinki). The investigator, or authorized designee, is responsible for obtaining written informed consent from each Patient using the Institutional Review Board (IRB) approved consent form prior to initiation of any study specific assessments or procedures.

The background of the proposed study, the potential benefits and risks, and all other legally required elements shall be carefully explained to the patient.

Before undergoing protocol required assessments, the subject or their legal representative must give witnessed written consent to participate in the study using the informed consent form approved by the Sponsor and clinical site's IRB.

A copy of the signed consent form shall be given to the subject with the original filed at the site.

Patients will be given adequate time to review the consent form, ask questions, and consider their options before being asked to sign the form. Informed consent shall be obtained under circumstances that minimize the possibility of coercion or undue influence. The information that is given to the patient shall be in language understandable to the patient. The patient will not be led to believe that they are waiving their rights as a study patient or the liability of the sponsor or investigator.

Patients will be informed that the Sponsor and regulatory authorities will have access to personally identifying information for the purposes of monitoring data against source documentation. However, all data stored and presented by the Sponsor will be de-identified.

If new information regarding the investigational device becomes available and/or the clinical investigational plan (CIP) changes and the information can significantly affect a Patient's future health and medical care, patients will be informed of the information and may be asked to sign a revised informed consent form.

The Sponsor and/or the IRB for the study site may alter or amend the text as appropriate, but both the IRB and the Sponsor must approve the final text of the informed consent before subject enrollment can begin. Any modification to the study sample informed consent form made by the Investigational Site must be approved by the sponsor and the IRB before use. Each Investigational Site will provide the sponsor with a copy of the IRB approved consent forms.

7.3. Randomization Assignment: Acoustic Enhancer with Ureteroscopic Laser Lithotripsy (Investigational Arm) vs. Standard Ureteroscopic Laser Lithotripsy (Control Arm)

Following consent and if a subject meets the study's inclusion/exclusion criteria, the subject will be randomly assigned to the investigational or control arm on the day of the procedure. If the potential subject does not meet the study procedure eligibility criteria, he/she will NOT be randomly assigned to treatment or the control arm. Random assignment will be conducted using an allocation ratio of 1:1 with one subject randomized to the Investigational Arm for each subject randomized to the Control Arm. Random assignment will be conducted block design generated separately for each clinical site. Subjects will be blinded to treatment allocation through index procedure.

7.4. Double Blinding

This study is a double blinded study in which:

- Study subjects will not be informed of their treatment allocation through the index procedure.
- In assessing stone fragmentation using a CT image as defined in the primary endpoint, an independent radiologist will conduct the assessment and will be blinded to the treatment allocation of each subject's CT image.

7.5. Point of Enrollment

After the patient signs the Informed Consent Form, all inclusion and exclusion criteria will be verified. If the potential subject meets all of the inclusion and none of the exclusion criteria, the potential subject will then become eligible for randomization. All subjects who sign the informed consent form will be entered in the Electronic Data Capture (EDC) system. Each site will assign a unique subject ID for each subject that signs an informed consent using three-digit site number and three-digit subject number. Each subject number will be assigned in consecutive order and will not be reused. Assigned subject numbers will be recorded on the Screening and Informed Consent Log (CAP-004-03). The Subject ID number will remain with the subject throughout the course of their involvement in the study. Those subjects who do not meet inclusion/exclusion criteria, withdraw consent prior enrollment, or were in the screening process while enrollment closed (also known as missed enrollment) will be appropriately documented in the EDC system.

Enrollment is defined as the time when the patient signs an IRB-approved informed consent form (thereafter becomes a study subject).

Potential subjects who fail to meet screening assessment requirements will be counted as a screen failure and will not be treated. Screen failure subjects will be exited from the study, and not evaluated for safety or effectiveness. Screen failures will be documented at the site on a screening log.

7.6. Subject Withdrawal or Discontinuation

Subjects may voluntarily withdraw from the study at any time for any reason. The Investigator(s) may elect at any time to withdraw a subject from the study for any reason unrelated to the study treatment if such a decision is in the subject's best medical interest. If a subject discontinues the study, or is withdrawn by the Investigator(s), as much follow-up data as possible will be obtained. The primary reason for termination or discontinuation will be documented on the Study Exit Form. Study subjects will be discontinued from the study if their stone could not be accurately assessed on the CT image. This subject would be considered a screen failure. Subjects who prematurely discontinue the study or are withdrawn from the study by the investigator after they receive general anesthesia will not be replaced.

Anticipated reasons for early termination of subject participation include:

- Subject Lost to Follow-Up: Unable to locate subject despite at least three documented attempts to notify the subject via telephone or e-mail, and by certified mail. A subject will not be considered lost to follow-up until the last scheduled follow-up visit (30 day follow up visit or 90 day follow up visit if subject has unresolved hydronephrosis).
- Subject's Withdrawal of Consent: The subject requests to terminate his/her involvement in the study, therefore withdrawing his/her consent to participate in the study (the investigator must thoroughly document the reasons for termination). Attempts will be made to retrieve any follow-up data, prior to the time point at which voluntary consent was withdrawn, when available, in particular regarding possible adverse events (AEs) at the time of study discontinuation.
- Subject Withdrawn by Investigator: Subjects who are withdrawn by the Investigator for any reason prior to study completion.
- Subject Death: If possible, an autopsy and/or death certificate should be obtained in order to document the cause of death.

Any subjects discontinued prior to receiving general anesthesia will be classified as screen failures and exited from the study and will not be included in any endpoint analysis.

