11.1. Adverse Event

An adverse event (AE) is any undesired clinical response or complication experienced by a subject. Monitoring and documenting of adverse events will begin at the start of the index procedure. When an adverse event is recorded as ongoing, an effort will be made to follow-up on the event at subsequent subject visits until the event is resolved or the subject exits the study.

CONFIDENTIAL Page 36 of 53

In this study, adverse events should be reported beginning at the time of administration of general anesthesia for the index procedure. Pre-existing conditions (recorded on the Medical History CRF), which occur during the study at the same severity as in the subject's history, should not be recorded as adverse events. Pre-existing conditions (recorded on the Medical History CRF) that worsen during the study OR a new episode begins must be recorded as AE(s). The onset date should be the start of the current episode or the date of the change in severity, not the onset date recorded on the Medical History CRF.

Upon enrollment, if a new adverse event is reported and subsequently determined to be medical history not previously documented, the information should be added to the medical history CRF. The event should be recorded as an AE only if there was a change in severity.

Intermittent Events

An AE that occurs intermittently at the same severity should be aggregated and recorded as one event unless, in the opinion of the Investigator, the events should be reported as discrete events (medical diagnosis terms).

- The onset date is the start of the first episode during the study.
- The resolution date is the end of the last episode (or may be persistent, if ongoing at the end of the study).
- The site should record "intermittent" in the AE description. If an intermittent event meets the regulatory criteria for seriousness, the associated frequency of the adverse event term (e.g., 4x/week) should be captured in the narrative/comment section of the CRF.
- If the event changes in severity or relationship to study device, it should be recorded as an AE update.

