2 STUDY DESIGN AND PROCEDURES

The clinical study is a prospective, multicenter, two-arm, randomized, double blinded study in male or female subjects 18 to 75 years of age with a diagnosis of urinary stone disease. For this study, double blinded means: 1) study subjects will not be informed of their treatment allocation through the index procedure, and 2) in assessing stone fragmentation using a CT image as defined in the primary endpoint, an independent radiologist will conduct the assessment and will be blinded to the treatment allocation of each subject's CT image.

The study visits consist of Screening, Treatment/Procedure [Day 1], Day 14 (+/- 4 days), Day 30 (+14 days), and Day 90 (+/- 21 days). Subjects who have unresolved hydronephrosis at Day 30 need to continue to Day 90. At 90-days post procedure, subjects who have on-going device and/or procedure-related serious adverse events (including device and/or procedure related hydronephrosis) and subjects with pre-existing (prior to treatment) hydronephrosis that have worsened or recurred will continue to be followed until the event has resolved or is deemed stable by the investigator prior to study exit. A total of 196 subjects will be enrolled in this study at up to 27 investigational sites located in the U.S., with each site enrolling no more than 20% of the total.

Following consent and if a subject meets the study's inclusion/exclusion criteria, the subject will be randomly assigned to the investigational arm (Acoustic Enhancer with URS-LL) or

control arm (URS-LL) on the day of the procedure. Random assignment will be conducted using an allocation ratio of 1:1 with one subject randomized to the investigational arm for each subject randomized to the control arm. A minimum of 176 evaluable subjects will be needed for analysis. After randomization and during procedure, eligibility criteria will be verified. If subjects are found to not meet eligibility criteria they will be considered screen failures and will not be considered randomized and treated for analysis purposes.

Random assignment will be conducted using a stratified permuted block design generated separately for each clinical site.

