6.1.3 Safety Population

The Safety population consists of all subjects who had a procedure performed. The Safety population will be used for the safety summaries (AEs) with groups based on the actual treatment received.

6.2 **PATIENT DISPOSITION**

The number of subjects included in each analysis population (ITT, Safety, and PP) will be summarized by treatment group and overall for all randomized subjects. The number of subjects screened, enrolled, randomized, randomized and not treated, completed the study, and discontinued the study early (including the reasons for discontinuation such as randomized and not treated due to a screen failure) will be summarized for each treatment group and overall.

Subjects who are excluded from an analysis population will be summarized by the reasons for exclusion by treatment group and overall.

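### The SAP's intraoperative screen-failure category may take anesthetized subjects out of safety follow-up and the safety rates, in conflict with Protocol 7.6 and 11.1

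*Protocol*

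**What the plan says.** **Who is a screen failure.** Protocol 7.5 says "Potential subjects who fail to meet screening assessment requirements will be counted as a screen failure and will not be treated", and then "Screen failure subjects will be exited from the study, and not evaluated for safety or effectiveness". Protocol 7.6 gives a cut-off: "Any subjects discontinued prior to receiving general anesthesia will be classified as screen failures". For later exits, the same section says that subjects who discontinue early or are "withdrawn from the study by the investigator after they receive general anesthesia will not be replaced", and it does not call them screen failures there.

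**What the SAP adds.** SAP 2 has eligibility verified after randomization and during the procedure. For subjects found ineligible at that stage, "they will be considered screen failures and will not be considered randomized and treated for analysis purposes". SAP 6.1.2 (Per-Protocol Population) adds that randomized subjects who fail screening intraoperatively are not in the analysis, and that information on them is listed only if the IRB or FDA asks. SAP 6.2 counts screen failures who were randomized but not treated among early discontinuations.

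**Safety data.** Protocol 11.1 says "adverse events should be reported beginning at the time of administration of general anesthesia for the index procedure". SAP 6.1.3, in the same words as Protocol 10.2, says "The Safety population consists of all subjects who had a procedure performed", with groups by treatment actually received. SAP 7 records as a separate item whether the URS-LL procedure could be performed.

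**The concern.** Protocol 7.6 and 11.1 fit together: the point at which screen failure stops being possible is the point at which adverse event reporting starts. SAP 2 moves the first boundary into the operation and leaves the second where it was. A subject can then be anesthetized, and so within adverse event reporting, and also carry a label that Protocol 7.5 ties to no safety evaluation.

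Three things are at stake.

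- **The safety rates.** Protocol 9.1 lists anesthesia, infection, ureteral damage and stricture risks. The anesthesia risks apply once a subject is anesthetized, and the others once the subject is instrumented. Protocol 6.6 makes study success depend on weighing safety findings against benefit, and SAP 12 plans no data safety and monitoring board.
- **Comparability of the arms.** Protocol 7.4 blinds only the subject and the CT reader. An eligibility call during surgery is therefore open to influence by knowledge of the arm, and losses could differ between arms.
- **Follow-up.** An infection or stricture can declare itself after the day of surgery. A subject exited on that day has no scheduled Day 14 call or Day 30 visit at which it would be recorded.

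**Working it through.** **1. The plan's own figure.** The only design figure is the 80% power for 55% versus 75% with 88 per arm at one-sided 0.025 (Protocol 10.3, SAP 3). With pooled variance under the null,

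z = [0.20 × √88 − 1.960 × √(2 × 0.65 × 0.35)] / √(0.55 × 0.45 + 0.75 × 0.25) = (1.876 − 1.322) / 0.660 = 0.840,

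which gives power of 79.96%. Also 176 / 0.9 = 195.6, rounded up to 196. Both figures reproduce. The present point does not depend on them.

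**2. The rules side by side, for a subject found ineligible under anesthesia.**

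| Source | Consequence for this subject |
|---|---|
| Protocol 7.6 | Past the stated cut-off for screen failure |
| Protocol 11.1 | Adverse events are reportable |
| SAP 2 | Screen failure; does not count as randomized and treated |
| SAP 6.1.2 | Outside the analysis; listed on request only |
| Protocol 7.5 | If a screen failure, exited and not evaluated for safety |
| Protocol 10.2, SAP 6.1.3 | In the Safety population if a procedure was performed; aborted procedures not addressed |

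The first two rows keep the subject, the next three can remove the subject, and the last can go either way. No passage says which rule prevails. Keeping the subject in the Safety population would not by itself restore follow-up: if Protocol 7.5 has ended the scheduled contacts, the subject stays in the denominator with less chance of an event being recorded. Grouping by actual treatment also leaves no clear group for someone whom SAP 2 does not count as treated. SAP 13 declares one change from the protocol's analyses and says there are no others, so the moved boundary is not acknowledged.

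**3. Size of a single event.** With 196 randomized 1:1 there are 98 per arm, and 1/98 = 1.0 percentage point.

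**4. Illustration under assumptions.** The documents give no rate of intraoperative screen failure. Assume that k = 2 to 10 exposed subjects are removed from one arm, each with event risk r = 2% to 10%. That range is the Protocol 9.1 band that includes kidney injury or infection needing further treatment, borrowed only for illustration.

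- Expected events lost = k × r: from 2 × 0.02 = 0.04 to 10 × 0.10 = 1.0.
- Chance of losing at least one = 1 − (1 − r)^k: from 1 − 0.98² = 4% to 1 − 0.90¹⁰ = 65%.

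Now suppose 3 events in 98 exposed subjects, with 5 subjects removed (exact 95% intervals):

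| Events among the 5 removed | Reported rate |
|---|---|
| No one removed | 3/98 = 3.1% (0.6% to 8.7%) |
| 0 | 3/93 = 3.2% (0.7% to 9.1%) |
| 1 | 2/93 = 2.2% (0.3% to 7.6%) |
| 3 | 0/93 = 0% (0% to 3.9%) |

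Removing event-free subjects barely matters. Removing subjects because the case went badly does.

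**The case against.** The strongest reply is that the protocol already protects these subjects. The Protocol 7.5 sentence follows one about people who fail screening assessments and are not treated, so alone it does not reach an anesthetized subject. SAP 2 speaks of analysis purposes, and SAP 1 refers the reader to the protocol for conduct. Protocol 7.6 asks for as much follow-up as possible from discontinued subjects, and Protocol 11 and 11.1 require procedural and post-procedural events to be recorded. The Safety population has no exception for screen failures. Exclusions would also be visible, because SAP 6.2 tabulates them by arm with reasons and the SAP 14.3 listings include screen failures.

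Much of this stands, and it rules out three stronger readings that a reader might infer.

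- **That these subjects' harms definitely leave the safety data.** The Safety definition and the adverse event rules could keep them. The documents support only that they may be lost.
- **That they will have received the device.** No passage describes Acoustic Enhancer being placed before ineligibility is found, and Protocol 10.2 says subjects ineligible at the time of the procedure are not treated under the protocol. It is equally true that no passage requires the check to be finished before placement.
- **That about 4 to 20 subjects are affected.** This comes from applying the 2% to 10% in Protocol 9.1 for failure to pass the ureteroscope to 196 subjects (3.9 to 19.6). Scope passage is not an eligibility criterion, so this counts a different group. SAP 7 summarizes whether URS-LL could be performed within the ITT population, which suggests those subjects stay in.

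The reply does not remove the conflict itself. General follow-up wording is weaker than scheduled visits, disposition counts do not restore events, and the status of an aborted procedure remains undefined.

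**Conclusion.** The point holds as a conflict between rules that needs to be reconciled. Through SAP 2 and 6.1.2, read with Protocol 7.5, anesthetized subjects may be lost from scheduled safety follow-up and from the safety rates. This contradicts Protocol 7.6 and 11.1 and, on one reading, the Safety population definition.

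How many subjects are affected is unknown. The effect is about 1 percentage point per event in an arm of 98; the larger shifts illustrated above rest on assumed counts and event risks. The concern about differences between arms rests on two inferences: that the surgeon, who is not among those blinded in Protocol 7.4, knows the allocation, and that the surgeon makes the intraoperative eligibility call. The change should be made because it is cheap and protects the safety comparison from exclusions after allocation, not because a large loss has been shown.

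**What to change.** 1. **Protocol 10.2 and SAP 6.1.3:** define the Safety population as all randomized subjects who received general anesthesia for the index procedure, which is where adverse event reporting already starts.
2. **Protocol 7.5, SAP 2 and SAP 6.1.2:** limit the screen-failure status that carries no safety evaluation to subjects discontinued before anesthesia, as Protocol 7.6 already has it. State that the intraoperative exclusion does not apply to the Safety population or to the existing adverse event collection at the Day 14 call and Day 30 visit. SAP 6.1.2 has to be amended with the others, or the conflict survives there.
3. **Safety tables:** show subjects whose procedure was aborted before lithotripsy or device placement on a separate line by randomized arm. Do not merge aborted investigational-arm cases into control, since that would load the control safety rate and flatter the device.

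The cost is wording in both documents and existing follow-up contacts for what should be a small number of subjects. The downside is that a few subjects without lithotripsy enter the safety denominators; the separate line makes them visible. The effectiveness populations do not change.
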